QD	once daily
RBC	red blood cell(s)
SAE	serious adverse event
SD	standard deviation
TAMA	therapeutic AhR-modulating agent
TEAEs	treatment emergent adverse events
t_{last}	time of last quantifiable concentration
t_{max}	time to maximum plasma concentration
ULN	upper limit of normal
V	visit
vIGA-AD™	validated Investigator Global Assessment for Atopic Dermatitis™
WBC	white blood cell(s)
[REDACTED]	[REDACTED]

Synopsis

Name of Sponsor/Company:					
Dermavant Sciences, Inc.					
Name of Investigational Product:					
DMVT-505 (tapinarof cream, 1%)					
Name of Active Ingredient:					
Tapinarof					
Protocol Number:	DMVT-505-2104	Phase:	2	Country:	United States and Canada
Title of Study:					
Open Label Maximal Use Study to Evaluate the Safety, Tolerability, and Pharmacokinetics of Tapinarof Cream, 1% in Pediatric Subjects with Extensive Atopic Dermatitis					
Study Center(s):					
Approximately 12 sites in the United States and Canada					
Objectives:					
Primary:					

• To evaluate the safety and tolerability of tapinarof cream, 1% once daily in pediatric subjects ages 2 to 17 years old with extensive atopic dermatitis (AD)• To evaluate the pharmacokinetics (PK) of tapinarof cream, 1% once daily in pediatric subjects ages 2 to 17 years old with extensive AD					
Secondary:					

• To assess the efficacy of tapinarof cream, 1% once daily in pediatric subjects ages 2 to 17 years old with extensive AD					
Methodology:					
This is a Phase 2a, multicenter, open-label, safety, tolerability and PK study in subjects ages 2 to 17 years with AD. The study will consist of three phases: Screening (up to 30 days), Treatment (27 days), and Follow-up (approximately 7 days). At Day 1 (Baseline), eligible subjects and/or their caregiver(s) will be instructed on how to apply tapinarof cream, 1% while under the supervision of site personnel in the clinic and have collection of PK samples to assess systemic absorption. During the treatment period, subjects and/or their caregiver(s) will apply tapinarof cream, 1% to affected areas once a day for 28 days, including newly appearing lesions and lesions/areas that improve during the study. Subjects or caregivers will apply sufficient study drug to cover completely each lesion with a thin layer of study drug and will record the time of study drug application and daily itch score (Peak Pruritus-Numeric Rating Scale [PP-NRS]) in a daily diary provided by the study site. (Note that subjects are allowed, but not required, to treat scalp lesions with study drug; however, efficacy analyses will not include assessment of AD in this area.) Subjects will return to the clinic on Days 8 and 28 for study assessments. On clinic visit days, subjects and/or their caregiver(s) will apply study drug under the supervision of site personnel. Additionally, subjects will be contacted by phone at Day 15 to assess adverse events (AEs) and concomitant medications, to review study drug administration instructions, and to confirm subject's continued participation in this study.					
At the end of the 27 days of treatment in this study, a final PK sample will be collected and subjects will have the option to enroll in a separate open label long-term safety study for an additional 48 weeks of treatment. Subjects who choose not to participate in the open-label long-term safety study or who fail to qualify for participation in the open-label long-term safety study will complete a Follow-up visit (Day 35) approximately 7 days after the end of treatment in this study. Subjects who withdraw from the study before Day 28 will complete an Early Termination Visit and are not eligible for the open-label long-term safety study. A follow-up visit will not be completed for a subject who completes an Early Termination visit.					
Subjects across the age range will be enrolled simultaneously. The blood sample collected at Screening will serve as the pre-dose plasma concentration.					
PK sampling will occur on Day 1 at 1, 3, and 5 hours post-dose. A single PK sample will be collected on Day 28. After 9 subjects have been enrolled (25% of the study), the PK data will be evaluated with the potential to eliminate the 5-hour post-dose sampling time point on Day 1.					

Number of Subjects:
Approximately 36 subjects ages 2 to 17 years old will be enrolled in the study with approximately 12 subjects, and a minimum of 10 subjects, enrolled into each of the three following age cohorts: 2-6 years old, 7-11 years old, 12-17 years old.
Diagnosis and Main Criteria for Inclusion:
Inclusion Criteria:
Each subject must meet all the following criteria to be eligible to participate in the study: 
1. Male and female subjects ages 2 to 17 years old with clinical diagnosis of AD by Hanifin and Rajka criteria.2. Subjects with AD covering $\geq 25\%$ of the body surface area (BSA) for subjects ages 12-17 years old, or $\geq 35\%$ of the BSA for subjects ages 2-11 years old. Scalp should be excluded from the BSA calculation to determine eligibility during Screening and at Baseline, and for all efficacy assessments.3. A Validated Investigator Global Assessment in Atopic Dermatitis (vIGA-ADTM) score of 3 or greater at Screening and Baseline (pre-dosing).4. AD present for at least 6 months for subjects ages 6-17 years old or 3 months for subjects ages 2 to 5 years old, confirmed by prior medical documentation and/or according to the subject and/or caregiver(s).5. Female subjects of childbearing potential who are engaging in sexual activity that could lead to pregnancy should use one of the following acceptable birth control methods while on study and for 4 weeks after the last exposure to study drug.
• Acceptable contraception methods include intrauterine device, hormonal contraceptives, barrier method (e.g., condom or diaphragm), or surgical sterilization of male partner (vasectomy)• Subjects who claim abstinence as their method of contraception are allowed provided they agree to use a barrier method (e.g., condom or diaphragm) should they become sexually active from Screening to 4 weeks after the last dose of study drugNon-child-bearing potential is defined as:
• Premenarchal• Pre-menopausal females with a documented bilateral tubal ligation, bilateral oophorectomy, hysterectomy, or hysteroscopic sterilization6. Female subjects of childbearing potential must have a negative serum pregnancy test at Screening and a negative urine pregnancy test at Baseline (Day 1).7. Subject, subject's parent(s), or legal representative must be capable of giving written informed consent, which includes compliance with the requirements and restrictions listed in the consent/assent form; written informed consent must be obtained prior to any study related procedures
Exclusion Criteria:
A subject who meets any of the following criteria will be excluded and considered ineligible for participation in the study: 
1. Concurrent conditions:
a. Immunocompromised (e.g., lymphoma, acquired immunodeficiency syndrome) or medical history of positive human immunodeficiency virus antibody at Screening.b. Chronic or acute systemic infection requiring treatment with, antiparasitics or antiprotozoals, within 4 weeks prior to the Baseline visit.c. Chronic or acute systemic bacterial infection requiring treatment with systemic antibiotics within one week prior to the Baseline visit.d. Chronic or acute superficial fungal infection requiring treatment with systemic antifungals within one week prior to the Baseline visit.e. Acute active bacterial, fungal, or viral (herpes simplex, herpes zoster, chicken pox) skin infection within one week prior to the Baseline visit; the condition should be completely resolved one week prior to Baseline Visit.f. Significant dermatologic or inflammatory condition other than AD that, in the Investigator's opinion, would make it difficult to interpret data or assessments during the study. For example, subjects with an active skin

condition such as Kaposi's varicelliform eruption, scabies, molluscum contagiosum, impetigo, psoriasis, severe acne, connective tissue disorder, or Netherton's syndrome, or any other concurrent active disease.

g. Concurrent skin lesions in the treatment area or pruritus due to conditions other than AD that, in the opinion of the Investigator, would either interfere with study evaluations or affect the safety of the subject.

2. Screening alanine aminotransferase (ALT) or aspartate aminotransferase (AST) $\geq 2.0 \times$ the upper limit of normal (ULN).
3. Screening total bilirubin $> 1.5 \times$ ULN; total bilirubin $> 1.5 \times$ ULN is acceptable if bilirubin is fractionated and direct bilirubin $< 35\%$.
4. Current or chronic history of liver disease, known hepatic or biliary abnormalities (with the exception of Gilbert's syndrome or asymptomatic gallstones), presence of hepatitis B surface antigen (HBsAg), or positive hepatitis C antibody test result, or presence of anti-hepatitis B core antigen (anti-HBc). Subjects having a negative HBsAg and a positive anti-HBc may enroll if they have a positive anti-hepatitis B surface antigen demonstrating natural immunity. Subjects with a history of hepatitis C virus infection who were medically cured and have an undetectable viral load are eligible to enroll. Subjects with a history of stable non-alcoholic fatty liver disease without evidence of active inflammation (elevated ALT/AST $\geq 2.0 \times$ ULN) or cirrhosis are eligible to enroll.
5. Current or a history of cancer within 5 years except for adequately treated skin basal cell carcinoma, cutaneous squamous cell carcinoma or carcinoma in situ of the cervix (surgical excision or electrodessication and curettage).
6. Subjects who would not be considered suitable for topical therapy (e.g., those with extensive disease involvement over a large BSA who would be candidates for systemic therapy).
7. Use of any prohibited medication or procedure within the indicated period before the Baseline visit.

NOTE: Prohibited concomitant medications, therapy, etc. during the defined period are as listed in the bullets below. If a subject requires any of these medications throughout the study period, he/she may be excluded from or discontinued from the study, at the discretion of the Investigator and Medical Monitor.

- a. From 4 months prior to Baseline until the completion of the Follow-up visit or study discontinuation:
 - DUPIXENT® (dupilumab) injection.
 - Any monoclonal antibody product that becomes approved for AD during the course of the trial.
- b. From 28 days prior to Baseline until the completion of the Follow-up visit or discontinuation:
 - Oral, injectable, and suppository preparations of corticosteroids. Eye drops and nasal preparations are allowed. Inhaled preparations are allowed when used for a stable condition and stable dose for ≥ 28 days before Screening and are continued at the same dose throughout the study.
 - Oral preparations and injections of immunosuppressants (cyclosporine, methotrexate, azathioprine, tacrolimus, Janus kinase inhibitors, etc.).
 - Excessive sun exposure, tanning booth, other ultraviolet light source and phototherapy including psoralen and ultraviolet A therapy or is unwilling to minimize natural and artificial sunlight exposure.
 - Treatment with antivirals with the exception of short-term treatment for acute upper respiratory viral infections (i.e., influenza) or viral suppressive therapy for a history of recurrent herpes labialis or genital herpes.
- c. From 14 days prior to Baseline until the completion of the Follow-up visit or discontinuation:
 - EUCRISA® (crisaborole) and any other PDE4 inhibitor.
 - Tacrolimus ointment and pimecrolimus cream.
 - Topical corticosteroids that are classified as medium or high potency (e.g., fluocinonide, triamcinolone acetonide) or super-high potency (e.g., clobetasol propionate). Eye drops and nasal preparations are allowed.
 - Coal tar products (on the body). If subject chooses to treat scalp with study drug, then coal tar products are prohibited for use on the scalp.

- Over the counter or herbal medicines for AD (topical and oral preparations). If subjects are using emollients, they may continue to use the same emollient on nonlesional skin during the study. Emollients containing salicylic acid are prohibited during the study.

d. From 7 days prior to Baseline until the completion of the Follow-up visit or discontinuation:

- Topical corticosteroids that are classified as low potency (e.g., desonide, hydrocortisone).
- Oral, injectable, or intravenous antibiotics or antifungal medications.
- Topical doxepin, topical gentamicin, or topical neomycin sulfate.
NOTE: Oral doxepin is allowed for treatment of depression if subject has been on a stable dose (4 weeks) at Screening.
- Topical products containing urea, except for the treatment of follicular events
- Antihistamines/antiallergics (oral, topical and injections): diphenhydramine, chlorpheniramine maleate, hydroxyzine.
NOTE: The following antihistamines are allowed from Screening throughout the treatment period: loratadine, fexofenadine hydrochloride, cetirizine hydrochloride. Subjects are allowed to switch from non-allowed antihistamines during Screening but must be on a stable dose for 7 days prior to Baseline.

e. The subject has received an investigational product within the following time period prior to the first dosing day in the current study: 30 days or 5 half-lives of the investigational product (whichever is longer).

8. A history of or ongoing serious illness or medical, physical, or psychiatric condition(s) that, in the Investigator's opinion, may interfere with the subject's participation in the study, interpretation of results, or ability to understand and give informed consent.

9. Pregnant females as determined by positive serum (Screening) or urine (Baseline) human chorionic gonadotropin test.

10. Lactating females.

11. History of sensitivity to the study medications, or components thereof or a history of drug or other allergy that, in the opinion of the Investigator or Medical Monitor, contraindicates their participation.

12. Previous known participation in a clinical study with tapinarof (previously known as GSK2894512 and WBI-1001).

Investigational Product, Dosage and Mode of Administration:

Tapinarof cream, 1% is a white to off-white cream containing 1% weight/weight (10 mg/gram) tapinarof, supplied in 30 gram tubes, and is to be administered by the subject and/or caregiver(s) once daily via topical application of a thin layer to affected areas.

Reference Therapy, Dosage and Mode of Administration:

n/a

Duration of Treatment:

Study duration for subjects who complete this Phase 2a study and do not enroll in the open-label long-term safety study is approximately 9 weeks in total (including approximately 30 days for Screening, 27 days of treatment, and a 1 week follow-up period).

Criteria for Evaluation:	
Pharmacokinetic Assessments:	
 Plasma concentrations of tapinarof
Safety Assessments:	
 AEs Vital signs Physical examinations Clinical laboratory tests Investigator-assessed Local Tolerability Scale (LTS)
Efficacy Assessments:	
 vIGA-AD™ Eczema Area Severity Index (EASI) Percentage of total body surface area (%BSA) affected PP-NRS for completion by subjects ages \geq 12 years and for completion by caregivers of subjects ages $<$ 12 years
Study Endpoints:	
Primary:	

 Incidence, frequency, and duration of treatment emergent adverse events (TEAEs) and serious adverse events (SAEs) Change from Baseline in laboratory values Change from baseline in vital signs Mean Investigator-assessed LTS scores by visit (overall and sensitive areas) Tapinarof plasma PK parameters on Day 1, if data permit, including: 
 area under the plasma concentration versus time curve from time zero to the last quantifiable concentration (AUC_{0-last}) maximum plasma concentration (C_{max}) time to maximum plasma concentration (t_{max}) time of last quantifiable concentration (t_{last}) Tapinarof plasma concentration on Day 28 	
Secondary:	

 Change in vIGA-AD™ score from Baseline at each study visit Proportion of subjects who have a vIGA-AD™ score of clear or almost clear (0 or 1) at each study visit Proportion of subjects with \geq50% improvement in EASI score from Baseline at each study visit Proportion of subjects with \geq75% improvement in EASI score from Baseline at each study visit Proportion of subjects with \geq90% improvement in EASI score from Baseline at each study visit Mean change and percent change in EASI score from Baseline at each study visit Mean change and percent change in %BSA affected from Baseline at each study visit Mean change and percent change in BSA x vIGA-AD™ values from Baseline at each study visit Proportion of subjects with a Baseline PP-NRS score \geq 4 who achieve \geq 4-point reduction in the PP NRS from Baseline at each study visit Proportion of subjects \geq 12 years old with a Baseline PP-NRS score \geq 4 who achieve a \geq 4-point reduction in PP-NRS score from Baseline at each study visit Proportion of subjects 2 to $<$ 12 years old with a Baseline PP-NRS score \geq 4 who achieve a \geq 4-point reduction in PP-NRS score from Baseline at each study visit Mean change in PP-NRS score from Baseline to Day 28 at each study visit by age group 	
Statistical Methods:	
Safety Analyses:	

 Analyses of the safety endpoints will be based upon the Safety population, which is defined as all enrolled subjects who receive at least 1 application of study drug. 	

- AEs will be summarized as incidence rates of any AEs, TEAEs, AEs of special interest, treatment-related TEAEs, TEAEs leading to study drug discontinuation, TEAEs leading to study discontinuation, and SAEs.
- Changes in laboratory parameters and vital signs will be summarized using shift tables and descriptively for quantitative measures by visit.
- LTS scores will be summarized by visit.

Pharmacokinetics:

- Plasma concentration data will be listed and summarized by study visit. PK parameters will be presented in tabular and/or graphical format and summarized descriptively if data permit

Efficacy Analyses:

- Analyses of efficacy endpoints will be based upon the Safety population. Proportions will be summarized using frequency counts and percentages, and mean changes and percent changes will be summarized using descriptive statistics (mean, median, standard deviation, minimum and maximum).

Schedule of Assessments

Table 1: Schedule of Assessments

Procedures and Assessment	Screening	Treatment Phase					FU ^a	ET ^b
	V1	V2	V3	P/C	V4	V5	NA	
	Day -30 to Day -1	Baseline, Day 1	Day 8 (±1 day)	Day 15 (±2 days)	Day 28 (±2 days)	Day 35 (±3 days)	NA	
Informed consent	X							
Inclusion and exclusion criteria	X	X						
Demography	X							
Fitzpatrick skin type	X							
Brief physical exam ^c	X	X	X			X	X	X
Medical history ^d	X	X ^e						
Pregnancy test (females of child-bearing potential) ^f	X	X ^g				X		X
Blood sample for clinical laboratory assessments ^h	X					X	X ⁱ	X
Urinalysis	X					X	X ⁱ	X
Vital signs ^j	X	X	X			X	X	X
Study drug Dispensation / Collection ^k		D	C/D			C		C
Review instructions for study drug application ^l		X	X	X				
Dispense/collect subject diary of study drug application		D	C/D			C		C
Tapinarof cream administration in-clinic under site supervision ^m		X	X					
PK samples ⁿ	X	X				X		
AE/SAE review	X	X	X	X	X	X	X	X
Concomitant medication review	X	X	X	X	X	X	X	X
vIGA-AD TM score ^o	X	X	X			X	X	X
%BSA affected ^p	X	X	X			X	X	X
EASI ^p		X	X			X	X	X
LTS assessment by Investigator ^q		X	X			X		
PP-NRS (assessed pre-dose at visit, as applicable) ^r		X	X			X		
Enrollment (optional) in open-label long-term safety study						X		

- a. The Follow-up Visit will be performed for any subject who fails to qualify for participation in the open-label long-term safety study or qualifies to participate in the open-label long-term safety study but elects not to enroll in that study. A follow-up visit will be not completed for a subject who terminates early.
- b. Subjects who withdraw from the study before Day 28 (Visit 4) will complete an Early Termination Visit.
- c. Physical examination will include height and weight, (BMI will be calculated in the CRF); a brief physical examination will be performed at other visits.
- d. Medical history will include month and year of AD diagnosis. As part of the subject's medical history, all systemic (oral and injectable) medications used by the subject for treatment of AD prior to 30 days before the Screening visit will be collected.
- e. Record any changes to medical history and document changes in source and EDC.
- f. Serum pregnancy test to be performed at the Screening visit only and urine pregnancy test to be performed at subsequent clinic visits when pregnancy testing is being performed.
- g. Urine pregnancy test to be performed before dosing.
- h. Clinical laboratory assessments include serum chemistry and liver chemistry tests, and hematology.
- i. If needed for ongoing AE or laboratory abnormality from previous visit.
- j. Vital signs will include systolic and diastolic blood pressure, pulse rate, and body temperature and should be measured after the subject is seated for at least 5 minutes. Vital signs will be measured before blood collection for clinical laboratory assessments and PK analysis.
- k. Site personnel will weigh the tubes to be dispensed and will record the weight of all tubes dispensed at each visit in the drug accountability logs. Site personnel will weigh the returned tubes (used and unused) and record the weight in the drug accountability logs. If a tube has been lost, discarded, or forgotten by the subject, then the site personnel will make a notation of this on the drug accountability logs.
- l. Subjects and/or caregivers will be instructed to apply study drug once daily at the approximate same time each day, based on subject and/or caregiver(s) preference.
- m. At all clinic visits, study drug will be applied after all safety and efficacy assessments have been conducted.
- n. The blood sample collected at Screening will serve as the pre-dose plasma concentration. PK sampling will occur on Day 1 at 1, 3, and 5 hours post-dose. A single PK sample will be collected on Day 28.
- o. The vIGA-AD™ assessment should be performed before the %BSA and EASI assessments.
- p. The subject's scalp should be excluded from the %BSA and EASI calculation.
- q. The LTS assessment should be conducted pre-dose.
- r. PP-NRS daily itch diaries will be dispensed at Day 1 (Baseline) and Day 8 and collected on Day 28.

%BSA = percent of total body surface area; AD = atopic dermatitis; AE = adverse event (s); BMI = body mass index; BP = blood pressure; C = study drug collection; CRF = case report form; D = study drug dispensation; ET = early termination; EASI = Eczema Area and Severity Index; Hep = hepatitis; HIV = human immunodeficiency virus; HR = heart rate; LTS = Local Tolerability Scale; NA = not applicable; P/C = phone call; PK = pharmacokinetic; SAE = serious adverse event; vIGA-ADTM = Validated Investigator Global Assessment in Atopic Dermatitis

1 Introduction

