5.4 Compliance with Study Drug Administration

At Baseline, study staff will provide the subject and/or caregiver with detailed instructions concerning protocol requirements and use of study drug. Additionally, subjects and/or caregivers will be asked to complete a daily diary with the time of each application of study drug, except on study visit days. At each post-Baseline study visit, study staff will review use of study drug, as applicable, with the subject. Subject compliance will be assessed via study diary completion.

When subjects are dosed at the site, they and/or their caregivers will apply the study drug under supervision of the study staff. The date and time of each dose administered in the clinic will be recorded in the source documents. In clinic doses are not recorded in the subject's daily diary. The study drug and study subject identification should be confirmed at the time of dosing by a member of the study site staff other than the person dispensing the study drug.

At the time of dispensing study drug to each subject, site personnel will weigh the tubes to be dispensed with the cap on and will record the weight of all tubes dispensed at each visit in the drug accountability logs.

Subjects and/or caregivers will be instructed to bring all used and unused tubes with them to each study visit. Site personnel will weigh the returned tubes (used and unused) with the cap on and record the weight in the drug accountability logs. If a tube has been lost, discarded, or forgotten by the subject, then the site personnel will make a notation of this on the drug accountability logs. Forgotten tubes should be returned by the subject at the next study visit. Tubes of study medication dispensed at the most recent prior visit which remain unopened (the foil cap on the tube remains fully intact/undisturbed) may be re-dispensed to study subjects at the current visit. Unopened tubes may only be re-dispensed once. Opened, partially used tubes or tubes with

foil overlay removed are not to be re-dispensed to study subjects. If there is any question as to re-dispensation, sites should issue new tubes of study medication to the subject(s).

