7.2 Visit 2; Baseline (Day 1)

On Day 1, subjects will be reassessed to confirm continued eligibility to participate in the study. All subjects who continue to meet study eligibility criteria will be enrolled and receive treatment.

The following additional procedures and assessments will be performed at the Baseline Visit:

- Brief physical exam
- Changes to medical history
- Urine pregnancy test (females of child-bearing potential)
- Vital signs measurement
- Dispense study drug
- Provide instructions on how to apply study drug
- Dispense study drug subject diary and PP-NRS diary
- Study drug application under supervision
- Blood sample collection for PK analysis
- AE recording
- Concomitant medication recording
- vIGA-AD™ score (excluding subject's scalp)
- %BSA affected calculation (excluding subject's scalp)
- EASI (excluding subject's scalp)
- LTS assessment by Investigator
- Assessment of itch (PP-NRS)

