12.2 Presentation of Plasma Concentrations

Individual plasma concentration results:

A raw data listing will be provided displaying the concentration as reported and the nominal and actual sampling times relative to start of dose administration (time since last dose). Results will be displayed using 3 significant digits.

Summary statistics of plasma concentrations:

The plasma concentrations for each analyte (i.e., tapinarof, tapinarof sulfate) will be summarized by nominal time point on Day 1 and Day 28 using descriptive statistics (n, arithmetic mean, standard deviation (SD), coefficient of variation (CV) % of arithmetic mean, median, minimum, maximum, geometric mean, and CV % for the geometric mean). The number of plasma concentrations that are BQL will be summarized by subject and the number and percentage of plasma concentrations that are BQL will be summarized overall.

Results will be displayed using 3 significant digits.

The CV % for the geometric mean will be calculated using the following formula:

$$CV (\%) = 100 * \sqrt{e^{SD^2} - 1}$$

where SD = standard deviation of the natural-log transformed data.

Figures:

Individual and mean concentration-time profiles on Day 1 will be provided on linear and semilogarithmic scales and may be presented with or without error bars. For individual concentration-time profiles, the actual sampling times will be used. Mean concentration-time profiles will be provided by age group and overall.

Overlaid individual and mean concentration-time plots on Day 1 for tapinarof and tapinarof sulfate will be provided in linear and semi-log scales.

Figures will be provided for the following relationships:

- Baseline %BSA of disease (x-axis) and Day 1 C_{max} (y-axis)
- Baseline %BSA of disease (x-axis) and Day 1 AUC_{0-t} (y-axis)
- Average grams of study drug administered per day (x-axis) and Day 1 C_{max} (y-axis)
- Average grams of study drug administered per day (x-axis) and Day 1 AUC_{0-t} (y-axis)
- Day 1 C_{max} (x-axis) and Day 1 C_{max} normalized by BSA (y-axis)
- Day 1 AUC_{0-t} (x-axis) and Day 1 AUC_{0-t} normalized by BSA (y-axis)

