13.1 Extent of Exposure

The following exposure and compliance parameters will be summarized descriptively:

- Total number of days exposed, defined as (date of last dose of study drug - date of first dose of study drug) + 1.
- Number of doses administered, calculated from the subject dose diary including in-clinic doses. If a subject is exposed to study drug for more than 1 day, and returns no diary records, then the total number of doses is regarded to be missing. Otherwise, for any day for which there is no diary record, it is assumed that no study drug was administered at home.
- Grams (g) of study drug administered, total and average per day. Drug administered is calculated as the summation of the difference between dispensed weight and returned weight for all returned tubes. Unreturned/unopened tubes will be assumed unused and will be included as 0 gram in amount drug used calculation.
- Percent compliance will be calculated as the $(\text{date of last dose} - \text{date of first dose} + 1 - \text{number of missed doses}) / (\text{date of last dose} - \text{date of first dose} + 1) * 100$. Number of missed doses will be based on data from the summary missed doses form.
- Subject compliance, defined as $\geq 80.0\%$ compliance while enrolled in the study. If the percentage of study medication compliance cannot be computed, the subject is assumed to be less than 80% compliant.

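### No required weighing isolates the supervised Day 1 dose, so the SAP's two figures of Day 1 Cmax and AUC against grams use a whole-period average in which Day 1 is about 1 of 27 doses

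*Protocol*

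**What the plan says.** **Weighing.** Protocol Table 1, note k: "Site personnel will weigh the tubes to be dispensed and will record the weight of all tubes dispensed at each visit", and then "Site personnel will weigh the returned tubes (used and unused) and record the weight in the drug accountability logs". Section 5.4 gives the same two occasions: "At the time of dispensing study drug to each subject, site personnel will weigh the tubes to be dispensed with the cap on", and again when tubes come back. Table 1 shows dispensing only on Day 1, collection and dispensing at Day 8, and collection at Day 28 or early termination.

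**In-clinic doses.** Section 5.4: "The date and time of each dose administered in the clinic will be recorded in the source documents". No amount is asked for. Section 7.2 lists "Study drug application under supervision" and PK blood collection on Day 1, with no weighing after the application.

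**Use in the analysis.** SAP 12.2 plans a figure of "Average grams of study drug administered per day (x-axis) and Day 1 C_{max} (y-axis"), and a companion figure with Day 1 AUC0-t. It also plots both parameters against baseline %BSA. SAP 13.1 defines grams as a total and an average per day: "Drug administered is calculated as the summation of the difference between dispensed weight and returned weight for all returned tubes". Tubes that do not come back are taken as unused and enter as 0 g. The SAP does not say whether the average is taken over days exposed or over doses administered.

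**The concern.** The dose in this trial is not fixed. Protocol 3.2 lets it follow the size of the affected area, so weight is the only direct measure of what was applied. Day 1 Cmax and AUC are primary PK endpoints. Protocol 1.1.2 says the study exists to measure exposure under conditions that maximise absorption, and Section 1.2 places the highest concentrations in the first week. The Day 1 samples, at 1, 3 and 5 hours, follow a single supervised application whose amount is not captured.

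In its place the SAP uses an average made up almost entirely of applications that had not yet happened when the blood was drawn. At stake are the reading of the two grams figures and the ability to say how much cream lay behind the measured exposure.

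**Working it through.** The plan has no power or precision figure to reproduce; the sample size rests on feasibility (Protocol 10.2, SAP 5).

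**1. Share of Day 1 in the plotted average.** Protocol 3.3 sets intended doses at the study day of the Day 28 visit minus 1, so 28 − 1 = 27. The Day 1 share is 1/27 = 3.7%. With the ±2 day window it runs from 1/29 = 3.4% to 1/25 = 4.0%.

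**2. Share of Day 1 in the first weighing interval.** Tubes dispensed on Day 1 and returned at Day 8 cover 7 doses: 1/7 = 14.3%. The Day 8 window is ±1 day in Table 1 and ±2 days in Section 7.3, and these need reconciling. Under ±2 days the share is 1/9 = 11.1% to 1/5 = 20.0%.

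**3. Correlation of the Day 1 amount with an m-dose average.** Assume that log grams are a subject's usual level plus independent day-to-day variation, and let r be the within-subject SD divided by the between-subject SD. The documents give no value for r. For the mean of log grams,

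correlation = √[(1 + r²/m) / (1 + r²)].

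| r (assumed) | m = 27 | m = 7 |
|---|---|---|
| 0.25 | 0.97 | 0.97 |
| 0.5 | 0.90 | 0.91 |
| 1 | 0.72 | 0.76 |

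For example, with r = 1 and m = 27: √[(1 + 0.037)/2] = 0.72. If the average relates to Day 1 Cmax only through the Day 1 amount, the true correlation is multiplied by this factor. Moving to a 7-dose average recovers little of this random loss; only a Day 1 weight removes it.

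**4. Drift in use.** If use falls linearly by a fraction f over 27 doses (assumed), the average is 1 − f/2 of the Day 1 amount. The first-seven-dose average is 1 − 3f/26 of it.

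| f (assumed) | 27-dose average / Day 1 | first 7 doses / Day 1 |
|---|---|---|
| 0.25 | 0.88 | 0.97 |
| 0.50 | 0.75 | 0.94 |
| 0.75 | 0.63 | 0.91 |

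Here the 7-dose average helps considerably.

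**5. Unreturned tubes.** One fully used 30 g tube counted as 0 g lowers the average by 30/(27 × g), if all 27 days stay in the denominator. At an assumed 5, 10 or 20 g/day that is 30/135 = 22%, 30/270 = 11% or 30/540 = 6%.

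**The case against.** **The primary results do not use grams.** AUC, Cmax, tmax, tlast and the Day 28 concentration are computed without them. A reader might infer that primary PK is compromised; the documents do not support that. This stands in full.

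**There is a Day 1 measure of extent.** SAP 12.2 plots Cmax and AUC against baseline %BSA, assessed before the first dose. This stands, but %BSA is not a dose. It excludes the scalp, which subjects may treat (Protocol 5.1.5), and it does not reflect layer thickness. The area normalisation in SAP 12.3 uses 185 cm² per 1% BSA for every age.

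**Drift is limited.** Protocol 5.1.5 keeps improved lesions under treatment, which restrains any fall in use. Lost, discarded or forgotten tubes are noted in the accountability logs, so affected subjects can be identified. Both stand. Missed doses dilute the average only if its denominator is days rather than doses, which the SAP leaves open.

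**Slope.** A reader might infer that the averaged x-axis flattens the exposure-dose slope. That holds if the log ratio of average to Day 1 grams is independent of Day 1 grams. With assumed log-SDs of 0.4 to 0.6 for Day 1 grams and 0.2 to 0.4 for the ratio, the slope factor would run from 0.16/(0.16 + 0.16) = 0.50 to 0.36/(0.36 + 0.04) = 0.90. But if Day 1 is one draw around a subject's usual use, as in step 3 of the working, the covariance of log Day 1 grams with the mean of log grams equals the variance of that mean. The slope of the first on the second is then 1, and only the scatter grows. The documents do not say which model applies, and the SAP plans no slope. No claim of flattening should be made.

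**Never weighed?** The documents show only that no such weighing is required. The annotated CRF and the Study Reference Manual are not available here.

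**Conclusion.** The point holds in a limited form. No weighing required by the protocol or SAP isolates the Day 1 application, and two planned figures set Day 1 exposure against an average in which Day 1 counts for about 3.7%. That mismatch follows directly from the documents.

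Its effect on the figures is a weaker correlation, of a size the documents do not fix: a factor of about 0.97 to 0.72 for assumed SD ratios of 0.25 to 1, with further error from any uneven drift and from used tubes counted as 0 g. The harm stops at those two descriptive figures and at any statement of the amount applied on Day 1. Minor to moderate priority.

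**What to change.** **If dosing can still be changed:** weigh every tube used at the supervised Day 1 application before and after it, record Day 1 grams in the CRF, and make Day 1 grams the x-axis of the two SAP 12.2 figures. The weight before application is already taken at dispensing, so the cost is one extra weighing per subject, on a scale already in use and by staff already supervising the dose, plus one CRF field.

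**If dosing is complete:** amend the SAP so that these figures use average grams per day from tubes dispensed on Day 1 and returned at Day 8, and label the axis as such. Flag subjects with unreturned tubes instead of entering those tubes as 0 g. Flag also tubes forgotten at Day 8 and returned later, since their weight may include later use. This needs no new data and removes most of the drift error, but it does not isolate Day 1.

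In either case, state the denominator of the average per day in SAP 13.1 and reconcile the two Day 8 visit windows.
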